Sample size overviews: The most complete data to obtain sample size estimates for our proposed study are derived primarily from studies of allergens and asthma. Based upon our calculations, we estimate that we will need at least 13 green buildings and 13 control buildings with at least 25 apartments in each building for a total $n = 650$ to detect differences in environmental exposures (notably allergens). In addition, we need at least 548 asthmatic children ($n=274$ in green and $n= 274$ in control buildings) to detect differences in asthma symptom days. With an anticipated loss to follow-up over a 1-year period = 20%, we will need at least 688 children with asthma (7-12 years) and 814 homes to assess exposure differences. We will enroll the children from 832 homes in order to ensure adequate power to detect both the asthma and exposure outcomes for the 13 study sites (i.e., 64 homes in each study site). The details of our sample size calculations are listed below and the equations that were used were from a book on longitudinal data analysis by Diggle, Liang, and Zeger (1994).

Sample size calculations for the overall difference between environmental exposures in green vs. control homes can be given as a simple test of two proportions and means; however a specific difficulty arises when trying to adjust for temporal and spatial correlations between measurements. A study that had enough measurements to assess spatial and temporal correlation was an integrated pest management (IPM) study conducted in New York

City (Chew et al. 2006; Kass et al. 2009). We have used the design effect from this study to estimate the number of clusters (or buildings) needed to detect differences in cockroach allergen because IPM is also one of the main green characteristics in the Green Housing Study. Assumptions from the aforementioned study comparing IPM to non-IPM homes are listed below:

- 1 13 buildings
 - 2 About half were treatment and the other half control
 - 3 3 repeated measures at: baseline (before IPM), 3months later (post-IPM), and 6months later (post-IPM)
 - 4 On average, 25 apartments within each building were measured
 - 5 For the control homes, the correlations between baseline and 3-month follow-up cockroach allergen measurements and 3-month and 6 months follow-up measurements were approximately equal to 0.5.
- Design effect due to clustering = 3.62

Equation 1. Sample size for repeated measures – cockroach allergen.

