$$m = D * [2(z_{\alpha} + z_{\rho})^2 \{1 + (n - 1)\rho\}] / (n\Delta^2)$$

m = number in each group (e.g., intervention and non-intervention)

n = number of repeated measurements (equals 3 in this scenario)

z_{α} = Z score for alpha = 0.05

z_{ρ} = Power, set at 0.80

ρ = correlation among repeated observations

$\Delta = d / \sigma$ where d is the smallest meaningful difference and σ is the standard deviation

D = Design effect due to clustering (This was not in the formula used by Diggle et al., but was added to adjust for clustering expected in our study)

Note: we also assumed a design effect (e.g., increase (multiplicative) sample needed because of the effects of clustering) equal to 3.62. This is the ratio in clustering sampling variance divided by the simple random variance (of the same size) (i.e., the denominator without clustering taken into account).

When calculating the sample sizes, we used two standardized effect sizes based on the IPM study: 0.37 and 0.30. The effect size of 0.37 is based on the ability to detect a difference of 0.8148 ln units of the *Blatella germanica* cockroach allergen (i.e., Bla g 2) and a standard deviation of ~ 2.2. The effect size of 0.30 is based on the ability to detect a difference of 0.649 ln units of Bla g 2 and a standard deviation of 2.2. We also assumed an alpha of 0.05 and a power of 80%). The sample size based on changing the expected correlation between repeated measures would result is presented in Table 8.

Assuming a correlation of 0.5 we get the following:

- 1 With assumption 1, we would need 16 buildings (8 green and 8 control) with at least 25 apartments per building
- 2 With assumption 2, we would need 26 buildings (13 green and 13 control) with at least 25 apartments per building.

Table 8. Sample size requirements for number of buildings.

Correlation between repeated measures	Sample size requirements (number of buildings)	
	Assuming Delta=0.377	Assuming Delta=0.30
0.2	6	9
0.3	7	11

0.4	8	12
0.5	8	13
0.6	9	15
0.7	10	16
0.8	11	17

*samples size is for each group (e.g., 8 buildings means 8 control and 8 green buildings)

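### Table 8 sizes the exposure comparison by buildings but uses normal quantiles: at its own inputs, 13 buildings per arm give about 77% power, not 80%

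*Protocol*

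**What the plan says.** In the Protocol, Section IV, Statistical Analysis and Related Issues, Equation 1 gives the number of homes per arm for the cockroach allergen comparison. It is a repeated-measures formula multiplied by a design effect of 3.62. The alpha term is defined as "Z score for alpha = 0.05" and power is set at 0.80. The design effect comes from an earlier integrated pest management study in 13 buildings, with about 25 apartments measured in each.

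The result is divided into buildings of 25 apartments and shown in Table 8. At correlation 0.5 the table gives 8 per arm in the column headed "Assuming Delta=0.377" and 13 per arm at 0.30. For the latter the text says: "With assumption 2, we would need 26 buildings (13 green and 13 control) with at least 25 apartments per building". The paragraph headed Sample size overviews adopts this, requiring "at least 13 green buildings and 13 control buildings with at least 25 apartments in each building".

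Neither Equation 1, Table 8 nor the text around them contains a t quantile, a degrees-of-freedom term or an added cluster per arm.

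**The concern.** Renovation type is treated here as a property of the building, and the Protocol expresses its requirement in buildings. On that unit, the error variance for green against control is estimated from 13 + 13 buildings, which leaves 24 degrees of freedom (14 for 8 + 8). A design effect makes the variance larger. It does not reflect that the variance is itself uncertain when so few clusters contribute to it. Normal quantiles treat the variance as known, so Equation 1 understates the number of buildings needed for a given power.

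What is at stake is the accuracy of a printed figure. The section on environmental exposures calls the resulting sample size conservative and adequate. On this point the calculation leans the other way.

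**Working it through.** **Inputs, all from Equation 1, Table 8 and the assumptions listed before them**
- Design effect D = 3.62
- Measurements n = 3, correlation rho = 0.5
- Apartments per building = 25
- Alpha 0.05, power 0.80
- Delta = 0.30 or 0.377. The text says 0.37 for the second, but only the table header's 0.377 reproduces the column: 0.37 gives 8.72 at rho = 0.5, which would round to 9.

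**Step 1: reproduce the plan's figures**

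m = D × 2 × (z_alpha + z_power)² × {1 + (n − 1)rho} / (n × Delta²), then divide by 25.

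With one-sided alpha, (1.645 + 0.842)² = 6.183 before rounding of the quantiles.
- Delta 0.30: 3.62 × 2 × 6.183 × 2 / (3 × 0.09) = 331.6 homes; 331.6 / 25 = 13.26, printed as 13.
- Delta 0.377: 3.62 × 2 × 6.183 × 2 / (3 × 0.1421) = 210.0 homes; 210.0 / 25 = 8.40, printed as 8.

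With nearest-integer rounding, all 14 cells of Table 8 come out this way. So the table rests on normal quantiles, a one-sided 5% level, and rounding down wherever the fraction is below one half.

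**Step 2: power at the printed building counts, by Z**

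For k buildings per arm, the expected test statistic is Delta / sqrt[2D{1 + (n − 1)rho} / (n × k × 25)].
- k = 13, Delta 0.30: 0.30 / sqrt(14.48 / 975) = 2.462. Z power = Phi(2.462 − 1.645) = 79.3%.
- k = 8, Delta 0.377: 0.377 / sqrt(14.48 / 600) = 2.427. Z power = Phi(2.427 − 1.645) = 78.3%.

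**Step 3: change only Z to t**

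The same values serve as the noncentrality of a t distribution on 2k − 2 degrees of freedom, still at one-sided 5%.

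| Buildings per arm | Delta | Z power | t power | df |
|---|---|---|---|---|
| 13 (adopted) | 0.30 | 79.3% | 77.2% | 24 |
| 8 (not adopted) | 0.377 | 78.3% | 74.6% | 14 |

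The shortfall from 80% at 13 per arm is 2.8 points: 0.7 from rounding 13.26 down (80.0 − 79.3) and 2.1 from Z versus t (79.3 − 77.2). At 8 per arm it is 5.4 points: 1.7 and 3.7.

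**Step 4: buildings per arm for at least 80% power at rho = 0.5**
- Delta 0.30: Z rounded up gives 14. By t, 14 per arm on 26 df gives 80.0%, so 14 is enough.
- Delta 0.377: Z rounded up gives 9. By t, 9 per arm on 16 df gives 79.3%, so 10 are needed.

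**Step 5: does the larger enrolment close the gap?**

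The plan enrols 32 homes per arm per city. After 20% loss, 32 × 0.8 = 25.6 remain, close to the 25 already used. Even with all 32 retained, the implied intraclass correlation of (3.62 − 1) / 24 = 0.109 raises the design effect to 1 + 31 × 0.109 = 4.38, and t power at 13 per arm is 79.2% on 24 df. More homes within the same buildings add no degrees of freedom.

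**The case against.** **The effect is small.** At 13 per arm the change from Z to t costs about 2 points. At Delta 0.30, correct rounding up alone already gives 14 buildings, and 14 also suffices by t. Normal-quantile planning formulas are a common approximation, and the other inputs are loose: moving the correlation from 0.5 to 0.45 would shift t power by about 1.8 points. All of this stands. It limits the weight of the point but does not make the printed 80% correct at the printed inputs.

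**The degrees of freedom are not fixed.** The site selection criteria allow a city to contribute several smaller developments, and the design fixes 32 homes per arm per city, not one building per arm. As an illustration, suppose two independent buildings of 12.8 retained homes per arm per city, with the same implied intraclass correlation. One-sided t power would then be about 93% on 50 df. A reader might infer that the trial itself cannot reach 80% power for exposures. The documents do not support that; the finding concerns the 13 + 13 calculation as written.

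**Matching by city.** Both arms come from the same development or neighborhoods, so a reader might treat the design as 13 city pairs and quote a still lower power on 12 df. That would charge the design for the lost degrees of freedom and give it no credit for the between-city variance that matching is meant to remove. The documents give no within-pair correlation, so no paired power can be stated.

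**Type I error.** A reader might also infer that the analysis will exceed its nominal level. The Protocol names hierarchical linear modeling and does not say that coefficients will be referred to the normal distribution. The reference distribution may properly be left to the SAP, so this is not a stated defect.

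**Conclusion.** The point holds as a modest correction to a printed calculation. At Table 8's own inputs and one-sided level, the adopted 13 buildings per arm give about 77% power, not 80%. About 2 points of the gap are due to normal quantiles with few buildings, and 0.7 to rounding down. The 8-per-arm option falls further, to 74.6%, but the plan does not rely on it.

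The result rests on the building as the unit, as Equation 1 and Table 8 use it, on one building per arm per city, on no credit for matching, and on the design effect and correlation taken from the earlier study. The one-sided level is only the level that reproduces the table; whether it was intended is a separate question.

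**What to change.** 1. Recompute Table 8 with t quantiles on building-level degrees of freedom and round up. At correlation 0.5 this gives 14 per arm (Delta 0.30) and 10 per arm (Delta 0.377).
2. If 13 per arm is kept, restate its power as about 77% at these inputs with one building per arm per city. Say that about 2 points come from Z versus t and 0.7 from rounding, and that the degrees of freedom change if a city contributes several buildings.
3. Add a sentence that green against control in the hierarchical model is tested on building-level degrees of freedom, for example by Kenward-Roger or Satterthwaite, so that the analysis matches the calculation.

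The cost is a revised table and two sentences. No buildings or homes need be added, because the proposal is to state the power of the adopted design correctly. The only downside is a slightly less favourable stated power. Any correction of the rounding or sidedness of the same table can be made at the same time.

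### Table 8 rounds minimum building counts to nearest, on an unstated one-sided alpha and with effect sizes that do not match the printed difference and SD; 13 and 8 buildings per arm should read 14 and 9 on that basis

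*Protocol*

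**What the plan says.** Section IV.d of the Protocol sizes the exposure comparison with Equation 1, a repeated-measures formula multiplied by a design effect. The stated inputs are:

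- "Design effect due to clustering = 3.62"
- "n = number of repeated measurements (equals 3 in this scenario"
- "Z score for alpha = 0.05", without saying whether one- or two-sided
- "We also assumed an alpha of 0.05 and a power of 80" per cent

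On effect size it says "we used two standardized effect sizes based on the IPM study: 0.37 and 0.30". The larger is described as 0.8148 ln units over an SD of about 2.2. For the smaller: "The effect size of 0.30 is based on the ability to detect a difference of 0.649 ln units", again with an SD of 2.2. The columns of Table 8 are headed 0.377 and 0.30.

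At a correlation of 0.5 the text reports 8 buildings per arm for the larger effect. For the smaller one it reports "we would need 26 buildings (13 green and 13 control) with at least 25 apartments per building". The sample size overview carries the second result forward as "at least 13 green buildings and 13 control buildings with at least 25 apartments in each building", total 650. It then allows for 20% loss (814 homes) and enrols 832, which is 32 homes per arm at each of 13 sites. The summary of sample size for environmental exposures describes this enrolment as conservative.

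**The concern.** A required number of clusters is a minimum, so a fractional result has to be rounded up. Rounding 13.26 to 13 or 8.40 to 8 gives a design slightly below the power it is said to have. The smaller-effect row matches the 13 buildings per arm and the 650 homes on which the exposure enrolment rests.

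The protocol also defines Delta as the difference divided by the SD, prints both parts, and then uses Deltas that do not equal the quotient. A reader cannot tell which of the three numbers was used. Because the sidedness of alpha is not given, the reader also cannot tell what the 80% refers to.

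**Working it through.** **Inputs** (Protocol IV.d): D = 3.62, n = 3, rho = 0.5, power 80% (z = 0.842), 25 apartments per building. Alpha is 0.05, with z = 1.645 one-sided.

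**Formula:** m per arm = D x 2(z_alpha + z_power)^2 x {1 + (n - 1)rho} / (n x Delta^2); buildings per arm = m / 25.

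**Reproducing the printed figures, one-sided, rho = 0.5:**

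- Delta 0.30: 3.62 x 2 x (1.645 + 0.842)^2 x 2 / (3 x 0.09) = 331.6 homes, 13.26 buildings (printed 13).
- Delta 0.377: 210.0 homes, 8.40 buildings (printed 8).

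The whole of Table 8:

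| rho | 0.377: exact | printed | rounded up | 0.30: exact | printed | rounded up |
|---|---|---|---|---|---|---|
| 0.2 | 5.88 | 6 | 6 | 9.28 | 9 | 10 |
| 0.3 | 6.72 | 7 | 7 | 10.61 | 11 | 11 |
| 0.4 | 7.56 | 8 | 8 | 11.94 | 12 | 12 |
| 0.5 | 8.40 | 8 | 9 | 13.26 | 13 | 14 |
| 0.6 | 9.24 | 9 | 10 | 14.59 | 15 | 15 |
| 0.7 | 10.08 | 10 | 11 | 15.92 | 16 | 16 |
| 0.8 | 10.92 | 11 | 11 | 17.24 | 17 | 18 |

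All 14 cells match rounding to nearest; six are rounded down. A two-sided alpha matches neither column (10.66 and 16.84 at rho = 0.5). The formaldehyde rows of Table 9 point the same way: the printed 75 and 37 come out at 75.1 and 36.8 one-sided, against 95.3 and 46.7 two-sided.

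**Effect sizes from the printed difference and SD:**

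- 0.8148 / 2.2 = 0.370 (table: 0.377). One-sided: 217.5 homes, 8.70 buildings.
- 0.649 / 2.2 = 0.295 (text and table: 0.30). One-sided: 342.9 homes, 13.72 buildings.
- SD implied by the tabulated Deltas: 0.8148 / 0.377 = 2.161 and 0.649 / 0.30 = 2.163.

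**Power** = Phi( sqrt[ m n Delta^2 / (2D{1 + (n - 1)rho}) ] - z_alpha ). For m = 325 and Delta 0.30, one-sided: sqrt(325 x 3 x 0.09 / 14.48) - 1.645 = 0.817, giving 79.3%.

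| Homes per arm | Delta | One-sided | Two-sided |
|---|---|---|---|
| 13 x 25 = 325 | 0.30 | 79.3% | 69.2% |
| 325 | 0.295 | 78.1% | 67.8% |
| 416 less 20% = 332.8 | 0.30 | 80.1% | 70.2% |
| 332.8 | 0.295 | 78.9% | 68.8% |
| 14 x 25 = 350 | 0.30 | 81.9% | 72.4% |
| 350 | 0.295 | 80.7% | 71.0% |

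Enrolment needed before 20% loss, one-sided: 2 x 331.6 / 0.8 = 829 homes at 0.30 (within 832), and 2 x 342.9 / 0.8 = about 858 at 0.295 (above 832).

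**Sensitivity to cluster size.** D = 3.62 at 25 apartments implies an intracluster correlation of (3.62 - 1)/24 = 0.109. With 332.8 / 13 = 25.6 homes per cluster, D = 3.69 and one-sided power is 79.5% (0.30) or 78.3% (0.295).

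**Two-sided counts, rounded up:** 17 (16.84) or 18 (17.41) for the smaller effect; 11 (10.66) or 12 (11.05) for the larger.

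**The case against.** The strongest reply is that the design is adequate and the table merely untidy. It has four parts.

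1. Twenty-five apartments is a floor. The trial enrols 32 homes per arm per site, and after loss 332.8 remain against 331.6 required at Delta 0.30. This stands for Delta 0.30, with a margin of about one home per arm. It does not hold at 0.295, where 342.9 are required.
2. The SD is first printed as approximate, and both tabulated Deltas imply the same value, about 2.16. The SD may therefore be the rounded number and 0.30 the right Delta. This is a fair inference but not something the protocol says. It is a good reason not to rebuild Table 8 on 0.370 and 0.295 until the inputs are settled. It does not rescue 13 and 8, because 13.26 and 8.40 still round up to 14 and 9.
3. Allergens are measured at four rounds in this trial (Table 3), not three. With n = 4 and rho = 0.5 the formula gives 310.8 homes (12.4 buildings) at 0.30 and 321.5 (12.9) at 0.295, so 13 would suffice one-sided. That is not the calculation printed, which sets n at 3, and counting only the post-renovation rounds gives three again. Whether baseline should count is a separate question.
4. The 8-building scenario does not size the trial; 13 buildings of 25 give about 92% one-sided power for that larger effect. This stands.

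A reader might infer from the rounding that the trial fails its 80% target or needs more sites. The documents do not support that: on the protocol's one-sided basis and its stated Delta of 0.30, planned enrolment reaches 80.1%. A reader might also infer that 0.30 and 0.377 are simply roundings of the true values. But 0.377 is not a rounding of 0.370, and the common implied SD suggests another explanation.

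**Conclusion.** The point holds as an error in stated figures, with a small effect on its own. On the basis that reproduces Table 8, the minimums are 14 and 9 buildings per arm, not 13 and 8. The text and table disagree on the larger effect, and neither Delta in Table 8 equals the printed difference over 2.2. The shortfall at 13 x 25 homes per arm is 0.7 points (Delta 0.30) to 1.9 points (0.295). At planned enrolment after loss, the 80% target is just met at 0.30 and just missed at 0.295. There is no margin that would justify the word conservative.

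The unstated one-sided alpha matters far more than the rounding. If the tests are two-sided, the same enrolment gives about 69 to 70% after loss, and even 14 buildings of 25 give only 71 to 72%.

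These figures rest on the protocol's own formula, normal quantiles, D = 3.62, n = 3 and rho = 0.5. One-sidedness is inferred from the match to Table 8 and is not stated in the sample size section.

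**What to change.** With 13 sites and 832 homes unchanged:

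- Reconcile Delta with the difference and SD, and use the same values in text and table. If the SD was nearer 2.16, print that; if it was 2.2, use 0.370 and 0.295.
- State whether alpha is one- or two-sided.
- Then recompute Table 8 on that basis, rounding up. At rho = 0.5 this gives 14 and 9 buildings per arm if one-sided, and 17 to 18 and 11 to 12 if two-sided.
- Restate power for the planned size after 20% loss: about 79 to 80% one-sided, or about 69 to 70% two-sided.
- Remove the description of the exposure sample size as conservative, insofar as it rests on this calculation.

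The cost is a recomputed table and a less favourable power statement; no site or participant is added.

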We also estimated the sample size for detecting differences in pesticides and VOCs. To date, there is only one study of an intervention to decrease pesticide exposures that used objective measurements of pesticide levels in residential homes in a non-agricultural environment (Williams et al). This study was conducted in homes of Latina and African-American women living in low-income housing in New York. In the study, 25 homes underwent IPM as an intervention. The pesticide synergist, piperonyl butoxide, is unique to pyrethroid pesticides and this was an analyte that was measured in the study's air samples. We used their pre- and post piperonyl butoxide concentrations (pre = mean $1.66 \pm \text{s.e. } 0.71 \text{ ng/m}^3$ vs. post = mean $0.8 \pm \text{s.e. } 0.22 \text{ ng/m}^3$) for our calculations of sample size which are shown in Table 9.

To date, there is only one study comparing the VOC levels in newly-built green homes and conventionally-built homes; therefore, this was not a renovation like our proposed study. We calculated the sample size based on their measurements of formaldehyde in the two types of homes in their study. This study was conducted in Finland. In the study, 6 apartments in each type of building had air measurements for formaldehyde (green-built: mean = $13 \mu\text{g/m}^3$, s.d. = 4 vs. conventionally-built: mean $23 \mu\text{g/m}^3$, s.d. = 5). We calculated the sample size necessary to detect a decrease in 50%, 25%, and 15%, of the difference in formaldehyde levels observed in their two study groups (see Table 9).

Devos et al (1990) have suggested that the minimum level of an indoor irritant be set with a safety factor of 40 (Devos, Patte et al. 1990). Given that the American Conference of Governmental Industrial Hygienists (ACGIH) threshold limit value is $368 \mu\text{g/m}^3$, a minimum level of formaldehyde below which no irritant effects are expected is $9.8 \mu\text{g/m}^3$ (which is the CDC/ATSDR Minimum Risk Level, <http://www.atsdr.cdc.gov/ToxProfiles/tp.asp?id=220&tid=39>). Based upon Table 9, we believe that detecting differences of $9.8 \mu\text{g/m}^3$ should not be a problem with at least 37 homes in each study group.

Table 9. Calculations of samples sizes for VOCs and pesticides

Analyte	Design Effect	Effect Size (Δ)	Required Sample size (in each group)
Formaldehyde			
- 15% : $1.5 \mu\text{g/m}^3$	3.6	0.33	408
- 25% : $3.5 \mu\text{g/m}^3$	3.6	0.77	75
- 50% : $5 \mu\text{g/m}^3$	3.6	1.10	37

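### Table 9's 25% formaldehyde row is sized for 35% of the reference difference (75 homes per group; a true 25% needs about 147), and its piperonyl butoxide requirement of 418 per group exceeds the homes planned

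*Protocol*

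**What the plan says.** The relevant text is in the protocol, section IV, Statistical Analysis and Related Issues, in the part on pesticides and VOCs that leads to Table 9.

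- **Formaldehyde.** The inputs come from a Finnish study: "In the study, 6 apartments in each type of building had air measurements for formaldehyde", with mean 13 (SD 4) in the green-built and 23 (SD 5) µg/m³ in the conventional building. The targets are set by "We calculated the sample size necessary to detect a decrease in 50%, 25%, and 15%, of the difference in formaldehyde levels observed". Table 9 prints 15% as 1.5 µg/m³ (effect size 0.33, 408 per group), 25% as 3.5 µg/m³ (0.77, 75) and 50% as 5 µg/m³ (1.10, 37).
- **Piperonyl butoxide.** The source is a New York study: "In the study, 25 homes underwent IPM as an intervention". The protocol says "We used their pre- and post piperonyl butoxide concentrations", namely 1.66 (SE 0.71) before and 0.8 (SE 0.22) ng/m³ after. Table 9 prints a 0.8 ng/m³ decrease, effect size 0.33 and 418 per group.
- **Formaldehyde benchmark.** After citing a safety factor of 40 and a threshold limit value of 368 µg/m³, the text says "a minimum level of formaldehyde below which no irritant effects are expected is" 9.8 µg/m³, also called the Minimum Risk Level. It concludes that 37 homes per group are enough to detect a difference of that size.
- **Adequacy.** The summary of sample size for environmental exposures concludes that 832 homes should be adequate for exposure differences. The Overview splits these into 32 green and 32 control homes in each of 13 sites. The sample size overview anticipates 20% loss to follow-up.

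**The concern.** Two of the three formaldehyde rows follow the stated rule and one does not. The discrepancy carries through to the printed effect size and sample size, so it is more than a stray digit in the label. A reader who takes the row at face value would believe that 75 homes per group give 80% power for a quarter of the Finnish contrast. They give about 55%.

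Table 9 is the only sizing shown for VOCs and pesticides, and the protocol's regression section names both among the main outcomes. Its figures should therefore match their definitions, and the adequacy statement that follows should be consistent with them. For piperonyl butoxide it is not, because the printed requirement is larger than the number of homes to be enrolled.

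**Working it through.** **Formula.** Equation 2 of the protocol with one measurement per home: m = D × 2(z_α + z_power)² / Δ², where Δ = d/σ.

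**Inputs.** Power is 80% and alpha is 0.05 (Table 9 footnote; likewise "We also assumed an alpha of 0.05 and a power of 80"% in the allergen calculation), with no sidedness given. D comes from the allergen calculation, "Design effect due to clustering = 3.62", and is shown as 3.6 in Table 9. Formaldehyde σ = √((4² + 5²)/2) = 4.528.

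**Reproducing Table 9.** With one-sided alpha, 2(1.645 + 0.842)² = 12.365.

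| Row | d (µg/m³) | Δ = d/4.528 | 3.62 × 12.365/Δ² | Printed |
|---|---|---|---|---|
| 15% | 1.5 | 0.331 | 407.8 | 408 |
| 25% | 3.5 | 0.773 | 74.9 | 75 |
| 50% | 5 | 1.104 | 36.7 | 37 |

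Two-sided alpha gives about 518, 95 and 47, which does not match. The table was therefore computed one-sided, although it does not say so.

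**The 25% row.** The reference difference is 23 − 13 = 10 µg/m³.

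- The printed 3.5 is 3.5/10 = 35%.
- 25% is 2.5 µg/m³: Δ = 2.5/4.528 = 0.552 and m = 3.62 × 12.365/0.552² ≈ 147.
- Two-sided, m ≈ 186.
- Power of 75 per group for 2.5 µg/m³ is about 55% one-sided and 43% two-sided.

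**Piperonyl butoxide.** I assume that the standard errors rest on 25 homes at both time points.

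- SDs: 0.71 × 5 = 3.55 and 0.22 × 5 = 1.10. Pooled σ = √((3.55² + 1.10²)/2) = 2.628.
- Difference of the stated means: 1.66 − 0.8 = 0.86. Δ = 0.86/2.628 = 0.327 and m = 3.62 × 12.365/0.327² ≈ 418. Both printed figures are reproduced.
- The printed 0.8 is the post-intervention mean, not the decrease.

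**Against the homes planned.** Enrolled: 32 × 13 = 416 per group. After 20% loss: 416 × 0.8 ≈ 333.

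- Power at 333 for 0.86 ng/m³, one-sided: Φ(0.327 × √(333/(2 × 3.62)) − 1.645) = Φ(0.574) ≈ 72%.
- Smallest decrease detectable with 80% power at 333: (1.645 + 0.842) × √(2 × 3.62/333) × 2.628 ≈ 0.96 ng/m³.

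**The 9.8 µg/m³ benchmark.** 368/40 = 9.2; a result of 9.8 would need 9.8 × 40 = 392. For a 9.8 µg/m³ difference, Δ = 9.8/4.528 = 2.16 and m ≈ 10 per group, so 37 is more than enough.

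**The case against.** The strongest defence is that nothing turns on the 25% row. The protocol says that the cockroach allergen calculation informed the sample size, and it discounts the other studies because they lacked repeated measurements and drew on restricted groups. No sentence relies on the 75, and 147 or even 186 is well below 333. This stands, and it is why the point is minor.

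It can also be said that 3.5 µg/m³ may have been the intended target, in which case 75 is right and the percentage is wrong. The protocol cannot settle this. But both the text and the row label say 25%, so one of the two has to change.

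Three stronger readings are tempting and are not supported.

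- **The pesticide row is short by 65 homes per group.** A reader might put the labelled 0.8 ng/m³ into the formula and get an effect size of 0.30 and 483 instead of 418. But 0.33 and 418 follow from the stated means and standard errors, so only the label is wrong.
- **The reassurance about 37 homes fails.** It rests on the 50% row, which is computed correctly for 5 µg/m³ and more than covers 9.8. Using a no-effect concentration as a between-group difference is loose reasoning, but it does not overturn the conclusion.
- **9.8 is a miscalculation.** The text also identifies 9.8 as the Minimum Risk Level, so two sources may have been run together.

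On adequacy, the sponsor could answer that repeated measurements will add precision beyond Table 9's single-measurement formula. That may be so, but the protocol shows no such calculation for pesticides. Discounting the source study is a reason to give Table 9 little weight; it does not show that 418 is met.

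**Conclusion.** The point holds as a minor correction of stated figures. The 25% formaldehyde row is inconsistent with its definition. For a true 25% the requirement is about 147 per group, roughly twice the printed 75. That figure assumes the one-sided alpha inferred from the table; two-sided it is about 186.

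The piperonyl butoxide row has a wrong label and correct figures. Those figures show that the general adequacy statement does not hold for this analyte on the plan's own assumptions: 418 are needed, 416 are enrolled and about 333 are expected to remain. This rests on one-sided alpha, D = 3.62, 25 homes behind each standard error and one measurement per home. The benchmark of 9.8 against 9.2 is a matter of wording. Total enrolment of 832 does not depend on any of this.

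**What to change.** 1. Make the 25% row and its definition agree. Either print 2.5 µg/m³, effect size 0.55 and about 147 per group, or keep 3.5 µg/m³, 0.77 and 75 and change both the row label and the text to 35%.
2. State the sidedness of alpha under Table 9. If two-sided testing is intended, recompute every row; a true 25% row then needs about 186.
3. Relabel the piperonyl butoxide row as a 0.86 ng/m³ decrease and keep 0.33 and 418.
4. In the summary for environmental exposures, qualify the adequacy statement for piperonyl butoxide: at about 333 homes per group, one-sided with D = 3.62, power is about 72% for 0.86 ng/m³, or the detectable decrease at 80% power is about 0.96 ng/m³.
5. Reconcile 9.8 µg/m³ with 368/40 = 9.2, saying which source each figure comes from. The statement about 37 homes can stay.

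The cost is a few table entries and sentences. Design, enrolment and data collection do not change.
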